## SUMMARY

**Rationale:** Colorectal anastomotic leakage (CAL) following colorectal surgery remains surgeons' most feared complication with an incidence varying from 8-13%. Due to CAL, 30-day mortality, readmission rate and Length of hospital Stay (LOS) rise substantially. Worldwide, the main focus of research is directed towards optimization of surgical techniques and treatment of CAL as well determining relevant risk factors. However, little is known regarding possible strategies that can prevent development of CAL. The aim of this study proposal is to identify high risk factors intraoperatively using a Leakage Check procedure, a multifactorial checklist scored with the whole surgical team prior to making a colorectal anastomosis. This could result in an unambiguous protocol to identify high risk patients.

**Primary objective:** Determination of relevant and modifiable perioperative risk factors of Colorectal anastomotic leakage in a Leakage Check procedure, a multifactorial checklist, right before the creation of the anastomosis.

**Study design:** Prospective multi-center observational registration study. Perioperative Leakage Check procedure to register hemodynamic risk factors, postoperatively registration of CAL and postoperative complications.

**Study population:** Adult patients undergoing colorectal surgery with an anastomosis.

**Intervention:** None.

**Main study parameters/endpoints:** Deviating perioperative risk factors.

**Nature and extent of the burden and risks associated with participation, benefit and group relatedness:** There are no risks or additional burden. Benefit for the patient itself is expected since their perioperative status is monitored more securely.

## 1. INTRODUCTION

### **Colorectal anastomotic leakage (CAL)**

In colorectal surgery the only alternative for a stoma is a colorectal anastomosis by reconnecting the two ends of intestine. The problem that this procedure encounters is that this attachment can leak. The consequences of an anastomotic leak are well known amongst surgeons. Symptoms such as abdominal pain, palpitations, fever and a bloated abdomen along with characteristic blood tests, are indicative for urgent return to the operating table for re-opening of the abdomen. The surgery area needs to be washed out and a fecal diversion is necessary otherwise gastrointestinal contents can cause further complications. This is associated with a prolonged stay in the intensive care unit, and a mortality rate of approximately 10% to 15%. In addition, a suture leakage has been associated with an increased local relapse and a reduced survival after colorectal cancer surgery. The 30-day mortality as well as the readmission rate and Length of hospital Stay (LOS) rises substantially with CAL, thereby increasing the treatment costs.

Colorectal anastomotic leakage is an important topic in scientific research due to the severe consequences. A number of anastomotic studies resulted in a decline of leakage. Nevertheless, CAL remains a surgeons most feared complication with an incidence varying from 8-13%. Main research focus has been directed towards optimization of surgical techniques and determining relevant risk factors. Several studies put a lot of effort in using different materials wrapped around the connection area to prevent leakage. These have not been fully successful until now. Researchers are now aiming at early detection of CAL to intervene as quickly as possible, however prevention is preferred above early detection. Many of these factors, i.e. age and sex, can be identified preoperatively. Some of them have been included in a colon leakage score (CLS) to determine in advance whether an anastomosis or stoma should be constructed. The CLS is a list of risk factors derived from a systematic search that is pre-checked before all colorectal surgeries. It contains preoperative risk factors each with a value and predicts by means of a total score the CAL-risk. The only downside to this is that after determining a high CAL-risk, there is no possibility to change or improve the risk factors. There are pre-habilitation programs that improve the patient's preoperative status, focusing on the risk factors related to the patients' lifestyle. Sadly the effect on reducing the risk is very disappointing. There is a great deal of knowledge about risk factors, but because they are

largely non-modifiable they can only make a prediction and not help with the reduction of the leakage risk.

An optimal surgical environment proves to have a beneficial effect on the healing of the anastomosis. For instance, anesthesia could possibly reveal shared risk factors in relation to anastomotic healing, perfusion and ischemia. Other changes in hemodynamic parameters during surgery can also be related to the risk of CAL. The importance of individual perioperative hemodynamic parameters during surgery on the postoperative outcome is widely described in literature. This warrants the hypothesis that optimal perioperative hemodynamic parameters are relevant on the healing of an anastomosis. Studies show that a large number of parameters are out of balance during the operation. For example, the influence of an elevated glucose in non-diabetes patients or intraoperative hypotension has been associated with a higher risk for postoperative adverse events. A lot of risk factors for CAL are not taken into account yet, even though there is plenty of information available that suggests further research concerning these parameters. Modifiable factors that are able to be optimized. These parameters are not currently being explicitly monitored or optimized during the operation, in particular, while making the anastomosis. Additionally, optimal values for hemodynamic parameters are even hardly established.

Due to these modifiable factors more studies are gaining interest in a multidisciplinary approach to prevent surgical complications. Since CAL has a multifactorial etiology, it can be hypothesized that intervention in modifiable risk factors might lead to a reduction of the incidence of CAL. This suggests a close collaboration of the surgical and anesthesiological team is essential, making this the first attempt to construct a tool that could reduce the patients' risk of CAL intraoperatively.

Prior to this multicenter prospective cohort study, a systematic review was performed summarizing the preceding studies on (perioperative) risk factors. The summary contains a report of these parameters, how important they are and if they show deviations during surgery. It was used to compose the checklist for the Leakage Check procedure, providing guidance on the available knowledge on this topic.

### **Leakage Check procedure**

The Leakage Check procedure will monitor possible perioperative risk factors right before the creation of the anastomosis. If perioperative risk factors are identified in the observational study, a follow up study will be done with a renewed Leakage Check procedure. The detected deviating risk factors will then be optimized to hopefully improve the healing of an anastomosis. At this moment no specific protocol exists whether to decide perioperatively to construct an anastomosis or to apply a stoma. A perioperative Leakage Check procedure will possibly create uniformity and increases awareness amongst surgeons and anesthesiologists in their approach to perform an anastomosis. Using a Leakage Check procedure, the actual performance status of the patient will be identified more securely.

The final purpose of this study is to assess reduction of CAL. Awareness to CAL throughout the entire treatment process needs to be extended.

## 2. OBJECTIVES

### **Primary Objective:**

1. Identify both relevant and modifiable perioperative risk factors of Colorectal anastomotic leakage in a Leakage Check procedure, a multifactorial checklist, right before the creation of the anastomosis.

### **Secondary Objectives:**

2. Observe deviations of the parameters in the checklist during surgery.
3. Determine the extent of these parameters as risk factors of CAL.
4. Perceiving a possible reduction of CAL due to extra emphasizing of the hemodynamic factors.
5. Creating a profile identifying high risk patients perioperatively.
6. Increasing the awareness amongst surgeons of the influence of perioperative parameter changes for CAL.

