Statistics are used to calculate a possible difference between patient outcomes and deviations in perioperative parameters, by means of a chi-squared test. The patients are divided into two groups, with and without CAL complication. The final purpose of this study is to optimize the risk factors in a follow up study. The determined perioperative risk factors will be ascribed optimum values by using the results of the Leak Check-Study. Dividing the patients into leaking and non-leaking groups to determine the most average values for perioperative factors. These results can be compared with the so-called optimal values from the literature of the systematic review. From these results, a new Leakage Check questionnaire will be designed for in the follow up study, containing often aberrant and modifiable perioperative factors and their optimal range. It depends on the obtained results how the optimization will take place.

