### 4.4 Sample size calculation

In order to ensure there will be enough patients to properly evaluate the effect of optimizing perioperative risk factors on the incidence of CAL, we performed a power analysis. This sample size was calculated using a 2-sample test of proportions with the two primary subgroups being patients with de deviating perioperative parameters and patients without deviating perioperative parameters. Calculation of an initial sample size of >2000 patients, assuming a significance level of  $\alpha = 0,05$ , to achieve a power of 80% to detect a difference of  $\delta = 0,06$  between the subgroups, assuming a 8% leak in the group with deviating risk factors and 2% in the group without deviating risk factors.

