## **6. STATISTICAL ANALYSIS**

### **6.1 Statistical plan**

Evaluation of relationships between parameters deviations and leakage rates of anastomosis. Analyses for outcome will be performed on the 2 groups, one with CAL and a group without CAL. Data will be analyzed with Statistical Package for the Social Sciences software version 20 (SPSS Inc., Chicago, IK, USA).

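### Secondary objective 3 asks how strongly each parameter raises leak risk, but the only inferential method the protocol fixes is a chi-squared test, which does not measure strength

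*Protocol*

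**What the plan says.** Protocol section 2 lists as its third objective: "Determine the extent of these parameters as risk factors of CAL".

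Section 3 names the method: "Statistics are used to calculate a possible difference between patient outcomes and deviations in perioperative parameters, by means of a chi-squared test". The grouping follows: "The patients are divided into two groups, with and without CAL complication".

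Section 6.1 describes the analysis as "Evaluation of relationships between parameters deviations and leakage rates of anastomosis" and repeats the grouping: "Analyses for outcome will be performed on the 2 groups, one with CAL and a group without CAL". Beyond that it names only the software.

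Two other quantities appear. Section 3 plans a descriptive comparison, "Dividing the patients into leaking and non-leaking groups to determine the most average values for perioperative factors", which serves to set optimum values. Section 4.4 says "This sample size was calculated using a 2-sample test of proportions", with leak rates of 8% and 2% in patients with and without deviating parameters. For a 2×2 table that is the same test as an uncorrected chi-squared.

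The next checklist is to be built as one "containing often aberrant and modifiable perioperative factors and their optimal range".

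**The concern.** Extent is a question of size: how much higher is the leak risk when a deviation is present, and how precisely is that known? A chi-squared test answers whether an association is visible at all. Its p-value depends on the strength of the association, on how common the deviation is and on the number of patients. Two factors with the same p-value can differ widely in strength, and a stronger but rarer factor can have the larger p-value.

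The design would support the right quantity. This is a cohort, so leak risk can be estimated directly with and without each deviation. The protocol fixes a test and no estimate.

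At stake is the answer to objective 3 and, through it, which parameters are regarded as relevant when the follow-up study is planned. A non-significant result for a rare deviation could be taken as absence of risk although a large increase has not been excluded.

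**Working it through.** **The plan's own figures.** The protocol gives no effect estimate per parameter, so there is none to reproduce. Its one calculation is the sample size in section 4.4. For 8% vs 2%, two-sided 5%, 80% power and equal groups, [1.96·√(2·0.05·0.95) + 0.842·√(0.08·0.92 + 0.02·0.98)]² / 0.06² = 206 per group, or 412 in total, against the stated figure of more than 2000. That gap is a separate matter. Only the planned number of patients is used below.

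**Inputs**
- N = 2000 (section 4.1).
- Overall leakage 8%, the low end of the 8–13% range in section 1. 13% is tried as well.
- Prevalence of each deviation and its risk ratio: assumed, because the documents give none per parameter.

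**Formulas.** With overall risk p, prevalence f and risk ratio RR:
- risk without the deviation: p0 = p / (f·RR + 1 − f); risk with it: p1 = RR·p0
- z = (p1 − p0) / √[p(1 − p)(1/n1 + 1/n0)]; for a 2×2 table, z² is the uncorrected chi-squared
- 95% CI for RR: exp{ln RR ± 1.96·√(1/a − 1/n1 + 1/c − 1/n0)}, with a and c the expected leaks in the n1 and n0 patients with and without the deviation

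**Common, weaker factor (f = 50%, RR 1.4)**
- p0 = 0.08/1.2 = 6.7%, p1 = 9.3%; difference 2.7 points
- standard error = √[0.08·0.92·(1/1000 + 1/1000)] = 0.01213
- z = 0.02667/0.01213 = 2.20, chi-squared 4.83, **p = 0.028**
- a = 93.3, c = 66.7; 95% CI for RR 1.04 to 1.89

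**Rarer, stronger factor (f = 5%, RR 1.6)**
- p0 = 0.08/1.03 = 7.8%, p1 = 12.4%; difference 4.7 points
- standard error = √[0.08·0.92·(1/100 + 1/1900)] = 0.02783
- z = 0.04660/0.02783 = 1.67, chi-squared 2.80, **p = 0.094**
- a = 12.4, c = 147.6; 95% CI for RR 0.93 to 2.75
- smallest expected count 100·0.08 = 8, so the chi-squared approximation is acceptable
- power = Φ[(0.0466 − 1.96·0.02783)/0.03356] = Φ(−0.24), about 41%, where 0.03356 is the unpooled standard error √[p1(1 − p1)/n1 + p0(1 − p0)/n0]

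The factor with the larger risk ratio and the larger risk difference has the larger p-value.

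**At 13% leakage**, same assumptions:
- f = 50%, RR 1.4: 15.2% vs 10.8%, z = 0.0433/0.01504 = 2.88, p = 0.004
- f = 5%, RR 1.6: 20.2% vs 12.6%, z = 0.0757/0.0345 = 2.19, p = 0.028

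Both now fall below 0.05, but the weaker factor still has the smaller p-value.

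**Whole-number tables, 160 leaks in 2000**

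| Deviation present | Leaks with vs without | Chi-squared | p | RR (95% CI) | Risk difference |
|---|---|---|---|---|---|
| 50% | 98/1000 vs 62/1000 | 8.80 | 0.003 | 1.58 (1.16–2.15) | 3.6 points |
| 5% | 15/100 vs 145/1900 | 7.01 | 0.008 | 1.97 (1.20–3.22) | 7.4 points |
| 2% | 8/40 vs 152/1960 | 7.99 | 0.005 | 2.58 (1.36–4.88) | 12.2 points |

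All three are significant, yet chi-squared puts the weakest first while the risk ratio and risk difference put it last.

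**Limits of the illustration.** In the 2% row the smallest expected count is 40·0.08 = 3.2, below the usual 5, so an exact test would be preferred there. The reversal is also not universal: one more leak in the 2% group (9/40 vs 151/1960, RR 2.92) gives chi-squared 11.66, above the common factor.

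**The case against.** The strongest reply is that the effect measure accompanying a named test is ordinary SAP or reporting detail. Section 3 does not say that only p-values will be shown, section 6.1 refers to leakage rates, and section 4.4 already thinks in terms of leak rates by exposure. The 2×2 table behind a chi-squared test contains both leak risks, so grouping by outcome loses no information. This stands in part: nothing is lost in the data, and a separate SAP may supply the estimates. It does not remove the mismatch, because the protocol does not leave the method open. It names a test for a question the test cannot answer, and commits to no estimate or interval.

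A reader might infer three stronger things, none of which the documents support.

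- **That factors will be ranked by chi-squared or dropped at p < 0.05.** No such rule is stated. The one stated selection principle for the next checklist is that factors be often abnormal and modifiable, so prevalence is partly a deliberate criterion.
- **That chi-squared is the only quantity in the plan.** Group averages are also planned. For continuous items they describe a difference in level, though not the size of the leak risk.
- **That a crude risk ratio settles objective 3 completely.** In an observational cohort that also records preoperative risk, it gives the size of the crude association and leaves confounding open.

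It is also fair that the prevalences and risk ratios above are assumed, and that an interval does not raise the power for a rare factor. It does show that the question is still undecided.

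**Conclusion.** The point holds as a mismatch between objective and method. Followed as written, the stated test does not deliver the extent that objective 3 asks for, and the protocol names no effect measure or interval that would.

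The size can only be illustrated. With 2000 patients, 8% leakage and assumed prevalences, a risk ratio of 1.4 can give p = 0.028 while a risk ratio of 1.6 gives p = 0.094, with an interval reaching 2.75. This shows how the results could be misread. It does not show that the sponsor will misread them, and other assumed values give no reversal. The mismatch itself does not depend on any assumed number.

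The concern bears on a secondary objective in an exploratory study, and the data needed are already being collected. It should be corrected, but it does not threaten the study.

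**What to change.** In sections 3 and 6.1, add for each Table 2 parameter that has a defined deviation:

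- leak risk in patients with and without the deviation;
- the risk difference and the risk ratio (or odds ratio), each with a 95% confidence interval, beside the test;
- an exact test where an expected count is below 5.

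State that objective 3 is answered from these estimates, and that a non-significant result is not read as absence of risk. No formal exclusion margin is required. Table 2 items with no evident deviation, such as the hospital or the type of operation, fall outside this rule.

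The cost is protocol wording and a little more analysis, with the data collection unchanged. The downside is that some rare factors will be reported as undecided.

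### Objective 5 promises a profile of high-risk patients, but the stated analyses give no combined risk for a patient and no check on factors chosen from the same data

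*Protocol*

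**What the plan says.** Secondary objective 5 (Protocol, section 2) is "Creating a profile identifying high risk patients perioperatively". The Summary expresses the same hope for the checklist: "This could result in an unambiguous protocol to identify high risk patients".

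The analysis is described in two places. Section 3 says: "Statistics are used to calculate a possible difference between patient outcomes and deviations in perioperative parameters, by means of a chi-squared test". It adds a descriptive step: "Dividing the patients into leaking and non-leaking groups to determine the most average values for perioperative factors". Section 6.1 speaks of evaluating how deviations relate to leakage, and then: "Analyses for outcome will be performed on the 2 groups, one with CAL and a group without CAL".

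Three other places bear on the point:

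- Section 3 has preoperative risk screened with the colon leakage score. The Introduction describes that score as a set of weighted preoperative factors whose total predicts leakage risk.
- Section 4.4 sizes the study on patients with versus without deviating parameters, and section 5.1.2 lists the total number of deviating factors as a secondary parameter.
- On later use, section 3 says: "From these results, a new Leakage Check questionnaire will be designed for in the follow up study".

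**The concern.** A profile that identifies high-risk patients is a statement about prediction. It needs a risk for a patient who shows a given combination of findings, and a figure for how well that risk separates leakers from non-leakers. Testing or averaging one parameter at a time supplies neither. Several Table 2 items (MAP, inotropics, blood loss, fluid balance, local perfusion) plausibly carry overlapping information, so their separate results cannot simply be added up.

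Two further gaps follow. The colon leakage score is collected before surgery, but no stated analysis asks whether the intraoperative items add anything to it. And if factors are picked because they look different in these patients, their apparent performance in the same patients is too good. The protocol describes no correction for this. The planned follow-up study is meant to optimise selected factors, not to validate a profile.

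At stake is whether objective 5 can be answered, and whether a reader could tell a useful profile from a chance one.

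**Working it through.** **1. Stated analyses set against what objective 5 needs**

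| Need | What the stated analyses give |
|---|---|
| Risk with one deviation | Yes: in a cohort, a 2x2 table gives a crude leak risk with and without it |
| Risk with any deviation | Yes, crudely, from the grouping in section 4.4 |
| Risk from a patient's combined findings | Not stated |
| Discrimination or calibration | Not stated |
| Gain over the preoperative score | Not stated, although the score is collected |
| Correction for selection, or validation | Not stated |

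**2. The protocol's own sample size**

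Section 4.4 gives more than 2000 patients for 8% versus 2%, alpha 0.05, "to achieve a power of 80" per cent. With equal groups, two-sided, and mean proportion 0.05:

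n per group = [1.960 x sqrt(2 x 0.05 x 0.95) + 0.842 x sqrt(0.08 x 0.92 + 0.02 x 0.98)]² / 0.06² = (0.604 + 0.257)² / 0.0036 ≈ 206, or 412 in total.

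The stated figure therefore does not reproduce at an equal split. About 2000 needs a very uneven split that is not stated, for example about 3.8% of patients deviating (total 2002). For the present point, what matters is that the calculation covers one two-group contrast and does not size a prediction profile.

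**3. Information available for a profile**

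Table 2 appears to list 5 + 5 + 1 + 8 = 19 items. Its layout is broken, so 18-20 is assumed. With 2000 patients and the quoted incidence of 8-13%:

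- events: 2000 x 0.08 = 160 to 2000 x 0.13 = 260;
- events per item: 160/19 = 8.4 to 260/19 = 13.7, before any item is split into categories.

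**4. How often chance alone would give a profile**

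This step assumes that items with chi-squared p<0.05 are kept. The protocol states no such rule. If the items are independent and none is related to leakage:

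- expected false selections among 19: 19 x 0.05 = 0.95;
- P(at least one) = 1 - 0.95^19 = 0.62 (0.60 for 18 items, 0.64 for 20).

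**5. How good a chance profile would look**

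Studies of 2000 patients were simulated with about 19 independent null binary items, an assumed prevalence of 10-25% each, and leakage of 8-13%. Items with p<0.05 were kept and added into a score, which was assessed in the same patients and in new ones.

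- Datasets yielding a profile: about 58-65%.
- Mean apparent AUC in those datasets: about 0.53-0.56.
- Mean AUC in new patients: 0.50.

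If datasets with no selected item are counted as 0.50, the mean apparent AUC is about 0.52-0.53.

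**The case against.** The strongest reply is that modelling detail normally belongs in a statistical analysis plan, which is not shown, and that section 6.1 excludes no multivariable model. Absence of detail alone would indeed be no finding. The point stands because the protocol does state a method, and that method, followed as written, does not deliver its own objective.

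Several stronger readings are tempting, and the documents do not support them.

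- *The plan yields no risk estimate at all.* Too strong: single-factor and any-deviation risks are available. The total number of deviating factors in section 5.1.2 could also be read as a per-patient count, a simple joint summary needing no data-driven selection. That wording is ambiguous, and nothing links the count to a risk or a performance figure.
- *The profile will be a list of significant factors.* The protocol gives no p-value rule. Testing each factor separately is a fair reading of sections 3 and 6.1, but not their wording. Steps 4 and 5 are conditional on it.
- *The follow-up checklist rests on the profile.* Section 3 says it will hold factors that are frequently out of range and can be changed. It does not mention the profile.
- *The optimism is as large as in a full joint model.* An unpenalised model of 19 null items (25% prevalence) shows an apparent c-statistic of about 0.60 at 8% leakage and 0.58 at 13%. The protocol plans no such model, so those figures do not measure its optimism.

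Two more replies carry weight. Section 5.2 says the items were chosen for proven predictive value, so a pure-noise scenario is a stress test and not a forecast. Objective 5 is also secondary, in a project the protocol calls exploratory, and the Summary's claim is hedged.

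**Conclusion.** The mismatch is real and of moderate size. Sections 3 and 6.1 state analyses that cannot produce objective 5's profile in any form that gives a patient's risk from combined findings, shows how well it performs, or shows what it adds to the preoperative score. If factors were chosen at p<0.05, about 58-65% of pure-noise datasets would still produce a profile, with an apparent AUC about 0.03-0.06 above its true 0.50. Those figures rest on 18-20 independent null items, an assumed 10-25% prevalence and 2000 patients; prevalence and independence are not document figures. The mismatch itself depends on none of them. It is worth correcting before analysis, but it does not undermine the single-factor comparisons.

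**What to change.** Add a paragraph for objective 5 to section 6.1:

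- Fit one multivariable logistic model of CAL, penalised or otherwise shrunk, given roughly 8-14 events per candidate item. Enter the preoperative colon leakage score first, then the Table 2 items, on their measured scale where available.
- Report discrimination and calibration with bootstrap optimism correction, repeating any selection step in every resample.
- Report the corrected gain in discrimination over the preoperative score with a confidence interval. Do not decide on the sign of the point estimate alone. In a simulation with 19 null items and one assumed real preoperative predictor (ridge-penalised, 120 runs), a rule of corrected gain above zero passed noise in 18-34% of studies at 8% leakage and 12-24% at 13%.
- Describe the profile as exploratory until it is validated in other patients.

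The chi-squared tests and group averages can stay for the other objectives. No new data or patients are needed. The cost is analysis text, modest programming, and reported performance less favourable than the uncorrected figure.
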